Anti-inflammatory therapy to improve outcomes in patients with chronic pancreatitis undergoing total pancreatectomy islet autotransplantation

Protocol Version: 2.2

Version Date: 08 August 2017

IRB#: 1602M84765

Primary Investigator:

[name] MD
University of Minnesota Health
[name]
[name]
[name]
[contact]
[contact]

Protocol Synopsis

Study Title	Anti-inflammatory therapy to improve outcomes in patients with chronic pancreatitis undergoing total pancreatectomy islet autotransplantation
Principal Investigator	[name]
Participating Site	University of Minnesota
Accrual Objective	Up to 60 patients with chronic pancreatitis undergoing total pancreatectomy and islet autotransplant (IAT) will be enrolled for screening. Up to 48 participants will be randomized to treatment, with accrual goal of 45 completing 90 days of follow up.
Study Design	Single center randomized, open-label
Study Duration	8 years (2.5-3 years recruitment + 5 years follow up)

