While endoscopic procedures are often employed as a first-line therapy, if ERCP procedures do not provide sufficient pain relief, surgical therapy including total pancreatectomy (TP) may be considered to relieve the root cause of pain. TP results in certain diabetes unless the islets are returned with autologous islet transplantation (IAT). In this procedure, the patient's pancreas is completely removed, mechanically and enzymatically digested with collagenase, and the islets are isolated and infused into the portal vein. The islets engraft and potentially survive long term in the liver, releasing insulin in response to glucose (6). IAT results in complete insulin independence in 1/3rd of patients. Another 1/3rd require only small doses of insulin, while the remaining patients are completely insulin dependent (4).

The field of TPIAT is growing, with improved acceptance of this procedure in the medical GI community. This is reflected in growth of the number of centers performing the procedure and the number of procedures performed within the past decade. With no medical therapies available to halt the progression of the disease, TPIAT is likely to remain the only treatment option for many patients, particularly those with debilitating small duct chronic pancreatitis. However, the high prevalence of postsurgical diabetes is a major barrier for many patients and providers in considering TPIAT for treatment of chronic pancreatitis. **By reducing the risk of diabetes after TPIAT, we have the opportunity to substantially increase the applicability of TPIAT as a treatment option for patients with severe chronic pancreatitis.**

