The proposed agents have shown promise in preclinical trials. In addition, etanercept has shown clinical efficacy in allotransplantation and the survival of marginal mass autologous islet transplants in non-human primates—a situation nearly analogous to TPIAT—are dramatically improved under simultaneous short-term administration of A1AT. However, no controlled clinical trials to date have been conducted in TPIAT using these agents. We have a novel opportunity to test these agents formally in clinical trials in TPIAT, using the large volume of patients with pancreatitis seen for this procedure at our institution.

[figure not shown]
While the primary indication for total pancreatectomy and islet autotransplant is to relieve pain and improve health-related quality of life (HRQOL), preventing or minimizing diabetes is an important secondary outcome which benefits recipients' long-term health and HRQOL

Because TPIAT is a major surgical procedure, with risk of diabetes, patients with chronic pancreatitis are carefully considered for this procedure by a multi-disciplinary team, and selected based on clear diagnosis of pancreatic disease causing pain, narcotic dependence or severely impaired quality of life, and failure to respond to maximal medical/ endoscopic therapy (19). Patients at our institution since 2007 have been enrolled in a prospective cohort study to follow pain symptoms, narcotic use, and HRQOL, in addition to diabetes outcomes, after this procedure. At 1, 2, and 3 years after TPIAT, 84-86% of patients report pain as resolved or significantly improved compared to before pancreatectomy. Mean summary scores for HRQOL obtained from the SF-36—a standardized HRQOL questionnaire— are 2 standard deviations below the population average for physical functioning and 1 standard deviation below the population mean for mental functioning before surgery, reflecting the severity of disease in this population, but improve by ≥ 1 standard deviation at 1 year and 2 years after TPIAT (7).

Insulin independence is observed in approximately 30% of patients at any given time between 1-3 years post-transplant (figure, below). Thus, there is significant room for improvement in diabetes outcomes after the IAT procedure. About 90% of patients have functioning islets, but this function is insufficient to achieve total insulin independence in many cases. Twenty percent of patients are unable to maintain their hemoglobin A1c level $< 7\%$

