Etanercept has been administered as part of multiple clinical trials in allotransplantation. The dosing regimen is extrapolated from the experience with islet allotransplantation, in which doses are administered on day 0, 3, 7, and 10. Although this short duration of treatment appears efficacious in islet allotransplantation, because TPIAT patients undergo a more significant surgical procedure than those patients who receive a cadaveric donor allograft infusion for type 1 diabetes (a relatively minor procedure with rapid recovery), we have extended the treatment duration in the TPIAT trial to 21 days.

PRIMARY AND KEY SECONDARY ENDPOINTS FOR THE STUDY

Primary Endpoint:

- 1) AIRmax from the Day 90 visit (obtained from glucose potentiated arginine-induced insulin secretion): We have data from UMN that supports this as the strongest correlate with beta cell mass, so this measure best addresses our research question. The early endpoint is chosen to rapidly translate pilot results into randomized clinical trials. Patients are not expected to achieve insulin independence in this population before day 90.

Key Secondary Endpoints:

- 1) Insulin independence: At day 365 and day 730. Defined as no insulin use for ≥ 14 days, with fasting blood sugar <126 mg/dL; 90 minute mixed meal glucose <180 mg/dL, and HbA1c $\leq 6.5\%$
- 2) Insulin dose (unit/day): At day 90, 365, and 730.
- 3) ACRmax, derived from GPAIS at days 90, 365, and 730
- 4) AIRglucose and ACRglucose, derived from the IVGTT at days 90, 365, and 730
- 5) AUC C-peptide from 2 hour MMTT, at days 90, 365, and 730
- 6) AUC glucose from 2 hour MMTT, at days 90, 365, and 730
- 7) Absence of severe hypoglycemic episodes (inclusive of day 90- 365) and HbA1c $<7\%$ at day 365
- 8) Absence of severe hypoglycemic episodes (inclusive of day 365-730) and HbA1c $<7\%$ at day 730

Key exploratory and safety endpoints:

- 1) Mean HbA1c by study group over the duration of the study
- 2) Number of patients experiencing at least 1 hypoglycemic event; and the incidence of SHE (events per subject-years) over the course of the study by study group

STUDY SUBJECTS

Study Subjects: inclusion and exclusion criteria to select suitable candidates for study

Inclusion Criteria

- 1) Age 18- 68 years. .

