Design and Methods to Evaluate Specific Aim #2

SPECIFIC AIM #2: To gather pilot data on the long-term impact of etanercept or alpha-1 antitrypsin administered during the peri-transplant period by evaluating islet function at 1 and 2 years post-transplant, as assessed by area under the curve for C-peptide on mixed meal tolerance testing (oral stimuli), acute insulin response to glucose-potentiated arginine stimulation (IV stimuli), and insulin requirements (units/kg/day) at 1 and 2 years post-TPIAT.

Hypothesis 1: AIRmax, AIRglu, and AUC C-pep from metabolic testing performed at yearly intervals post-transplant will be greater in the A1AT-treated patients and etanercept-treated patients, compared to controls.

Hypothesis 2: Mean daily insulin requirements (units/kg/day) will be lower in the A1AT-treated group vs control and in the etanercept treated vs control.

Hypothesis 3: AIRmax and AIRglu at 3 months will predict insulin independence at 1 year and 2 years post-transplant.

For specific aim #2, patients will return to the study center at day 365 ± 28 days and 730 ± 56 days post-transplant for repeat metabolic testing. Testing performed will be identical to that described under approach for specific aim 1. Both insulin use and the proportion of patients insulin independent will be recorded.

As an exploratory analysis, patients will continue to be followed yearly by a telephone or face-to-face visit, depending on whether they are returning to UMN for clinical care, at which time mean daily insulin use will be recorded, and records will be reviewed for home blood glucometer results, hemoglobin A1c level, and mixed meal fasting and stimulated glucose and C-peptide performed at the patient's local lab, per our usual routine for clinical follow up.

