This is a pilot, parallel-arm study to compare etanercept, A1AT, and control groups; the primary outcome is maximal potentiated arginine induced insulin secretion (AIRmax) measured at 90 days posttransplant. We propose to enroll 15 patients in each group which will give 80% power to detect a difference between any two groups of at least 1.06*(within-group standard deviation of the outcome). From preliminary data for AIRmax measured more than one year post-transplant, the study will have 80% power to detect a difference of at least 33 mU/mL in pairwise comparisons of AIRmax between each of the 3 groups, corresponding to a 24% increase over standard treatment (control group).

The table below shows estimated minimum detectable differences for main outcomes, based on means and standard deviations from preliminary testing performed at 1 year post-transplant (for IVGTT and MMTT) or beyond 1 year post transplant (GPIAS) in this population of TPIAT recipients.

Test	Derived Measure	minimum detectable difference	n	Mean	SD
GPAIS	AIRmax (mU/mL)	33	10	137	31
IVGTT	AIRglu (mU/mL*min)	162	33	169	153
	ACRglu (ng/mL *min)	8.8	36	9.8	8.3
MMTT	AUC C-peptide (ng/mL *min)	147	39	295	139
	AUC glucose (mg/dL *min)	3790	39	16,037	3,579

For specific aim 1, the primary outcome, AIRmax, and other measurements at day 90 will be compared between treatment groups with a linear model to adjust for transplanted islet mass and the randomization stratum, BMI (< or \geq 27 kg/m²). For aim 2, the same analysis will be performed for measurements made at 1 year and 2 years post-transplant. In addition, we will assess whether day 90 AIRmax and AIRglu measurements predict insulin independence at 1 and 2 years post-transplant using a logistic regression model. For aim 3, repeated measurements during the weeks immediately post-transplant will be summarized by peak and area under the curve for comparison by the same linear model used for aim 1, i.e., adjusting for transplanted islet mass and the randomization stratum. We will also compare the groups based on the longitudinal series of measurements using a mixed-effects linear model with fixed effects of treatment group, transplanted islet mass and randomization stratum, and a random intercept for each participant to model the correlation between repeated measurements from the same person.

POTENTIAL RISKS AND BENEFITS

Forseeable Risks

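### With about 13-15 expected events, an ordinary logistic fit would modestly overstate how strongly day-90 AIRmax and AIRglu predict insulin independence; a bias-reduced fit is a cheap improvement

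*Combined protocol and SAP*

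**What the plan says.** The analysis is given one sentence, in the section Sample Size and Plan for Data Analysis: "we will assess whether day 90 AIRmax and AIRglu measurements predict insulin independence at 1 and 2 years post-transplant using a logistic regression model". It serves Hypothesis 3 under Specific Aim 2, that "AIRmax and AIRglu at 3 months will predict insulin independence at 1 year and 2 years post-transplant".

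The plan does not state an estimator, an interval method, an expected event count, or whether AIRmax and AIRglu share a model.

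The size of the data set comes from elsewhere in the protocol:

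- The Synopsis plans up to 48 randomized, "with accrual goal of 45 completing 90 days of follow up". The target of 45 applies at day 90, so fewer may remain at years 1 and 2.
- The Background states that "Insulin independence is observed in approximately 30% of patients at any given time between 1-3 years post-transplant", and in another paragraph that "IAT results in complete insulin independence in 1/3rd of patients".
- The endpoint section defines insulin independence as a composite: at least 14 days without insulin, "with fasting blood sugar <126 mg/dL; 90 minute mixed meal glucose <180 mg/dL", and an HbA1c limit.

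**The concern.** Maximum likelihood estimates of log odds ratios are biased away from zero when events are few for the number of coefficients. Here there would be about seven events per predictor if both measures enter one model. The two tests are also run back to back on the same morning, and the Background says both measures track transplanted islet mass, so they are likely to be correlated.

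This model is the trial's own check that its 90-day measures relate to a clinical outcome. An inflated coefficient would make that relation look somewhat stronger than it is to anyone who reads the odds ratio at face value.

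**Working it through.** **The plan's own figure.** No power or precision is stated for the logistic model. The stated calculation concerns the group comparison: "We propose to enroll 15 patients in each group which will give 80% power to detect a difference between any two groups" of 1.06 SD. It reproduces. A two-sample t-test with 15 per arm, 28 degrees of freedom and two-sided 5% (assumed, not stated) has power 0.800 at 1.06 SD, and 1.06 × 31 = 32.9, matching the 33 mU/mL for AIRmax. It says nothing about the logistic analysis.

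**Expected events.**

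- At 30%: 45 × 0.30 = 13.5 (binomial 95% range 8-20).
- At one third: 45 / 3 = 15 (range 9-21).
- Two predictors in one model: 13.5 / 2 = 6.75 events per predictor.

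**Bias of the ordinary fit.** Data sets of 45 patients were simulated with a 30% event rate and standard-normal predictors, 10,000 sets per row. The log odds ratios per SD and the correlation are assumptions. Overstatement = (mean or median estimate ÷ true value) − 1. In joint rows both coefficients have the same true value.

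| Model | True log OR per SD | Mean, ordinary | Median, ordinary | Mean, Firth | RMSE, ordinary → Firth |
|---|---|---|---|---|---|
| One measure | 0.4 | +10.1% | +4.4% | +0.2% | 0.40 → 0.36 |
| One measure | 0.7 | +10.7% | +5.4% | +0.3% | 0.46 → 0.40 |
| One measure | 1.0 | +11.7% | +5.9% | +0.6% | 0.52 → 0.45 |
| One measure | 1.5 | +13.2% | +5.9% | +0.4% | 0.73 → 0.57 |
| Both, correlation 0.6 | 0.5 | +12.8 to +16.6% | +6.2 to +8.8% | −1.2 to +2.1% | 0.56-0.57 → 0.48-0.49 |
| Both, correlation 0.6 | 0.7 | +16.4 to +17.4% | +7.7 to +8.9% | +0.5 to +1.4% | 0.65 → 0.53 |
| Both, correlation 0.6 | 1.0 | +20.2 to +21.4% | +8.9 to +9.9% | +0.7 to +1.5% | 0.87-0.89 → 0.65 |
| Both, correlation 0.6 | 1.3 | +24.6 to +24.7% | +10.7 to +11.1% | +1.3 to +1.6% | 1.11-1.12 → 0.77-0.80 |

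With correlation 0.7 (3,000 sets per setting), a true 0.8 is estimated on average as 0.94-0.95, and 0.94 / 0.8 = 1.18. A true 1.2 is estimated as 1.46-1.51, and 1.46 / 1.2 = 1.22, 1.51 / 1.2 = 1.26. The Firth means are 0.81 and 1.20-1.25.

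On the odds ratio scale, a true 0.8 is exp(0.8) = 2.23. The average joint estimate of 0.94 corresponds to exp(0.94) = 2.56.

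**Sensitivity.** For the joint model at 0.7 per SD and correlation 0.5, mean overstatement is about 21% at a 20% event rate, about 15% at 40% and 14-16% at 50%. A skewed AIRglu, or 40 patients, widens the range for single coefficients to about 9-28%.

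**Size beside the noise.** The mean bias is 0.1-0.3 of the sampling SD in the settings above. In the joint model with true value 0.8 and correlation 0.7, the sampling SD is about 0.79.

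**Tests and intervals.** With no true effect, the ordinary Wald test at 5% rejects in 4.0% of sets with one predictor and in 3.8-4.9% with two (4,000 sets per setting). Wald 95% intervals cover the true value in about 95-98% of sets. Separation, where the ordinary estimate diverges, occurs in 0.5% of sets or fewer at a 30% event rate.

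**Cost of the bias-reduced fit.** Firth's penalty moves the mean predicted probability from 0.307, equal to the observed rate, to 0.316, a shift of 0.8 percentage points with rounding. Its profile-penalised test holds its size (4.4-4.5%).

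**The case against.** The strongest reply is that nothing in the planned inference breaks. Hypothesis 3 asks whether the measures predict insulin independence. The bias vanishes when there is no effect, so it creates no false positives, and coverage is sound. The percentages rest on effects and a correlation that the documents do not give. They are means of a skewed sampling distribution, and the medians are about half as large. The sentence in the plan is also compatible with Firth and with separate models. All of this stands, and it limits the point to the size of the reported association.

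The event count is also less certain than 13-15 suggests. The 30% comes from the centre's general cohort. The trial excludes patients with diabetes or raised glucose or HbA1c, which could raise the rate, while the composite definition and loss to follow-up could lower it. The direction of the bias is the same at every event rate tried from 20% to 50%.

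A reader might infer that the inflated odds ratios would mis-size the follow-on trial. The documents do not support that. AIRmax is justified by the centre's existing data and prior studies, the agent is to be chosen on day-90 graft function and mechanistic data, and Aim 2 is described as pilot data. Nothing says that this coefficient will size or justify the next study.

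A reader might also expect diverging coefficients to be a practical hazard. At the expected event rate they are rare.

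**Conclusion.** The point holds as a modest, inexpensive improvement to a secondary pilot analysis. With about 13-15 expected events (plausibly 8-20), an ordinary logistic fit overstates the log odds ratios on average by about 10-13% with one measure per model and about 13-25% with both together. At 1.2 per SD and correlation 0.7 the joint figure reaches about 26%. Median overstatement is about 4-13%.

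These sizes depend on assumed effects (0.8-1.2 per SD as the central case, with smaller and larger values tried) and an assumed correlation of up to 0.7. Detection, test size and coverage are not at issue, and the bias is small beside the sampling error. The case for acting is that the alternative nearly removes the mean bias and also lowers the RMSE, for example from 0.65 to 0.53 at 0.7 per SD in the joint model.

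**What to change.** Add to the Aim 2 paragraph of the analysis plan:

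- Fit by Firth (bias-reduced) logistic regression, with profile-penalised-likelihood confidence intervals.
- Report AIRmax and AIRglu in separate models as the main result, and the joint model as secondary. The two answer different questions: the joint coefficients describe what each measure adds given the other.
- If predicted probabilities are reported, apply an intercept correction, which removes the shift of about 1 percentage point.

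A bootstrap optimism-corrected area under the ROC curve would be a useful extra but is optional. If the bias-reduced fit is declined, the choice between joint and separate models should still be fixed in advance.

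The cost is a sentence or two in the plan, a software option and slightly smaller reported odds ratios. Sample size, data collection and clinical procedures do not change.

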The first hurdle to a successful islet transplant is the number of islets available, and thus the transplanted islet mass is an important predictor of subsequent diabetes risk (7-9, 21). However significant variability in diabetes outcomes is seen for any given transplanted islet mass. Approximately 70% of IAT recipients with >5000 islet equivalents (IEQ)/kilogram body weight transplanted will achieve insulin independence, while 30% never come off insulin despite the large number of islets infused. In contrast, nearly 10% of those patients with a very low islet mass (<2500 IEQ/kg) will maintain insulin independence, sometimes for years (7). This variability can largely be explained by the difference between the *transplanted* islet mass and the *engrafted* islet mass. Beta cell apoptosis and loss occurs in the immediate post-operative period due to the stress of the procedure and transplant environment. High levels of beta cell apoptosis are observed, particularly in the 7 days after surgery, with apoptosis observed even at 30 days (11, 12). It has been estimated that more than half of the islet mass may be lost in this early post-transplant period in islet transplant recipients (13). The innate inflammatory response, triggered by islet infusion, hypoxia, and hyperglycemic stress, is an important contributor to beta cell loss. In allograft transplant, successful engraftment of transplanted islets, as demonstrated by functional testing at 3 months, is strongly predictive of diabetes remission at 1 year, even more so than the initial number of islets transplanted (22). Thus, this is a critical early window in which to intervene to optimize engrafted islet mass.

Islets are damaged by inflammatory cytokines, which are expressed in the islet graft and upregulated in the TPIAT recipient immediately after surgery

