In order to adequately assess the impact of any therapy on islet engraftment, it is important to have endpoints that reflect islet mass. Because it is not possible to directly quantify the number of islets that engraft and survive in the liver post-transplant, we have carefully selected surrogate endpoints that reflect beta cell function and mass. We will assess several previously validated measures: 1) C-peptide response to a mixed meal tolerance test (MMTT), 2) the acute C-peptide and insulin response to intravenous glucose tolerance (IVGTT), and glucose potentiated arginine-induced insulin secretion (GPAIS).

The oral stimulus used most often in the TPIAT setting and in trials of new onset type 1 diabetes mellitus is the mixed meal tolerance test, in which the subject ingests a standard amount of Boost High Protein or a similar beverage. The MMTT is an accepted measure of beta cell *function* in islet transplant and diabetes studies (7, 71, 72), and it is simple to perform in the clinic setting. However, it may be less useful than the intravenous stimuli as a direct measure of islet *mass* (73). Intravenous stimuli—dextrose and/or arginine—have been shown to correlate with islet mass in animal and clinical transplant models (74-76). Both the acute insulin response to glucose (AIRglu) derived from the IVGTT and the maximal acute insulin response to arginine (AIRmax) measured from GPAIS correlate strongly with transplanted islet mass in patients who maintain euglycemia long-term (74). While transplanted islet mass is not the same as engrafted islet mass, these studies were performed in patients who were specially selected from those with optimal long-term beta cell function, and so were likely the recipients with the best engraftment. Thus, they appear to be reasonable surrogate measure for engrafted beta cell mass. Both measures were superior to a simple arginine stimulation test (22). In allotransplant patients, the AIRglu and AIRmax at 3 months post-transplant predicted insulin independence at 1 year. Thus, this test performed early after transplant was predictive of key long-term clinical outcomes (22).

Measures of islet loss

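### The logistic model for insulin independence tests whether day 90 AIRmax and AIRglu predict it, but cannot show whether they add anything to the transplanted islet count

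*Combined protocol and SAP*

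**What the plan says.** The section Sample Size and Plan for Data Analysis states, for Aim 2: "we will assess whether day 90 AIRmax and AIRglu measurements predict insulin independence at 1 and 2 years post-transplant using a logistic regression model". It lists no covariate for this model. The model serves Hypothesis 3 under Design and Methods to Evaluate Specific Aim #2: "AIRmax and AIRglu at 3 months will predict insulin independence at 1 year and 2 years post-transplant".

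The other models in the same section do name islet mass. Day 90 outcomes are compared "with a linear model to adjust for transplanted islet mass and the randomization stratum", and that analysis is repeated at 1 and 2 years and for the Aim 3 peaks and areas. The Aim 3 mixed model has "fixed effects of treatment group, transplanted islet mass and randomization stratum".

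The Background section on early engraftment says that "the transplanted islet mass is an important predictor of subsequent diabetes risk" and gives figures: "Approximately 70% of IAT recipients with >5000 islet equivalents (IEQ)/kilogram body weight transplanted will achieve insulin independence", against nearly 10% below 2500 IEQ/kg. The section on islet function as a surrogate for islet mass says that AIRglu and AIRmax "correlate strongly with transplanted islet mass in patients who maintain euglycemia long-term". Islet count is recorded for every participant (Aim 3 methods, islet graft assessments).

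**The concern.** By the documents' own account, islet mass is related to the outcome and to both candidate predictors. A day 90 test that merely echoed the number of islets infused would therefore be associated with insulin independence, and a model without islet mass cannot separate that from information about engraftment.

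The distinction matters because the protocol treats engraftment as function relative to islets infused. The Background attributes much of the spread in outcome at a given islet mass to the gap between transplanted and engrafted mass. Aim 1 Hypothesis 1 is worded as AIRmax relative to the islets transplanted. The Background also cites an allograft finding that 3-month function "is strongly predictive of diabetes remission at 1 year, even more so than the initial number of islets transplanted". This trial could examine the same question in autograft recipients with data it already collects. At stake is the interpretation of a positive result: whether it may be read as showing that the test tells more than the count.

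**Working it through.** **Plan's own figure.** None is given for the logistic model. The section's only power figure reproduces: with 15 per group and two-sided alpha 0.05 (assumed; not stated), a t-test has 80.0% power at 1.06 SD; 1.06 × 31 = 32.9 mU/mL and 33/137 = 24.1%. It does not bear on this point.

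**Inputs from the documents.** 45 patients; about 30% insulin independent in years 1 to 3, so 0.30 × 45 = 13.5, about 14 events; about 70% independent above 5000 IEQ/kg and about 10% below 2500.

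**Assumed inputs.** The correlation r between AIRmax and islet mass (0.3 to 0.8) and the distribution of islet mass.

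**Question put to the simulation.** Suppose AIRmax has no effect on the outcome once islet mass is known. How often is it significant at 5% (likelihood ratio test) without and with islet mass in the model?

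- *Set-up A.* Standardised islet mass z; logit(p) = −1.05 + 1.3z; AIRmax = r·z + √(1 − r²)·e, with e independent noise. Average 13.9 events; 4,000 datasets per row.
- *Set-up B.* Log IEQ/kg normal, median 3000, log-SD 0.6 or 0.7; intercept and slope solved to match the 70% and 10% figures, which gives 32% to 33% overall and 14.6 to 15.0 events; 2,000 datasets per row.

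| Assumed r | A: AIRmax, no islet mass | B: AIRmax, no islet mass | B: AIRmax and AIRglu jointly, no islet mass |
|---|---|---|---|
| 0.3 | 16% | 18–19% | 16–17% |
| 0.5 | 36% | 37–40% | 35–38% |
| 0.6 | 49% | not run | not run |
| 0.7 | 62% | 65–69% | 60–64% |
| 0.8 | 74% | 79–82% | 72–77% |

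The joint column also assumes a correlation of 0.7 between the parts of AIRmax and AIRglu that islet mass does not explain. Across the table the range is roughly 17% to 80%.

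With islet mass in the model the rate is 6% in A, and 7% (AIRmax alone) or 8% (joint) in B. It does not change with r, because the adjusted test uses only the part of AIRmax that islet mass does not explain.

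**What the adjusted model can detect.** Set-up A with r = 0.6 and a real added effect of AIRmax:

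- Odds ratio 1.5 or 2 per SD of AIRmax: the adjusted test is significant in 15% or 32% of trials.
- The same odds ratios per SD of the part of AIRmax not explained by islet mass: 21% or 47%.

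**Events per predictor.** One test plus islet mass: 14/2 = 7, the same as entering AIRmax and AIRglu together. All three: 14/3, about 5.

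**The case against.** The strongest reply is that Hypothesis 3 claims prediction and nothing more, and a model containing only the two tests answers that. This stands. A reader might infer from the table that the planned analysis would falsely confirm Hypothesis 3 in up to four trials in five. It would not. In set-up A with r = 0.6, AIRmax really does predict the outcome (population c-statistic 0.67), so the 49% is power for a true association. It is a false-positive rate only for a claim of added value, which the plan does not make.

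A reader might also infer that a positive result would carry AIRmax into the next trial. No section makes this model decide that. Objectives and Specific Aims bases the choice of agent on day 90 graft function and mechanistic data, and the endpoint is justified by its relation to beta cell mass and by speed. The allograft comparison with islet number is used to argue for the timing of treatment.

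Three further limits hold. The plan is silent on covariates here; it does not exclude them. Islet mass is documented as an important predictor and a correlate, the latter in patients chosen for good long-term function, and not as a proven driver of both. An AIRmax with no information beyond the count is a limiting case that the protocol's own account of engraftment speaks against.

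Finally, the adjusted test is weak, as the detection figures show. That rules out replacing the planned model. It does not rule out reporting a second one.

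**Conclusion.** The point holds as a limit on interpretation. The planned model can support the statement that the day 90 tests predict insulin independence. It cannot support the statement that they predict beyond the transplanted islet count.

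The direction follows from the documents for any positive correlation. The size does not: it depends on the assumed r, the assumed spread of islet mass and an event rate near 30%. That rate describes the centre's general experience, whereas the trial excludes pre-existing diabetes, and losses by years 1 and 2 would shrink the sample.

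The point is minor. It concerns a secondary analysis in an aim described as gathering pilot data.

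**What to change.** Keep the planned unadjusted model as the analysis of Hypothesis 3. Add the following to the analysis section:

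- For AIRmax and AIRglu separately, at 1 year and at 2 years, fit a second logistic model that also contains transplanted islet mass, using the same variable as the primary model. Islet count is recorded both in total and per kg, so name which.
- Report the adjusted odds ratio per SD with its confidence interval, and the gain over islet mass alone (likelihood ratio statistic and change in c-statistic).
- State that a positive unadjusted result does not show value beyond the islet count.
- State that, with about 14 events, the adjusted estimate is imprecise and a non-significant result is not evidence of no added value.

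Penalised likelihood is optional; it would guard against unstable estimates at this number of events.

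The cost is a few sentences and 2 × 2 = 4 further models. No new data, visits or patients are needed. The drawback is wide intervals, which the stated caution covers.
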